## **6.7 BASELINE, TIME WINDOWS AND CALCULATED VISITS**

For an overview on planned visits refer to Flow Chart in the CTP.

As a general rule, last assessment before first trial drug intake (included) will be used as baseline. If the baseline value is missing and the screening value is available, then the baseline value will be defined as the screening value taken closest to baseline date.

A windowing will be performed as described in [table 6.7:1](#) to [table 6.7: 6](#) in order to assign data to the relevant study visit based on the actual day of the assessment. Data will be analyzed using the re-calculated visits in the statistical tables. However, in the listings, all visits performed will be displayed (even if outside time-window), along with the re-calculated visit.

All visits, regardless whether study treatment is ongoing or not, and EOT visit are classified according to the time windowing rules. EOT is the day of the last trial drug administration (nintedanib and sildenafilfil/placebo).

Visits recorded as FUP visits will be classified according to the time windowing as given in the table for time windowing and will not keep their labeling “FUP”, unless they fulfill the conditions for the last category in the table.

If after windowing of visits at baseline, two values fall within the same baseline interval, then the last value will be taken into account. If after windowing of post-baseline visits, two visits fall in the same interval, then the measurement closest to the planned visit will be taken into account. In case two measurements are equidistant from the planned visit, then the last one will be picked. The same rules will be applied for laboratory measurements.

If after windowing of post-baseline visits, two values fall within the same interval “Follow-up”, then only the first value will be taken into account.

For visits of patients who continue to attend the scheduled study visits after early EOT visit the same rules apply as given above.

Table 6.7: 2 Time windowing rules for SGRQ, UCSD SOBQ, EQ-5D, Resting SpO2

Time window of actual day [1]			Allocated to		
Start day	End day (included)	Length of the time-window [days]	Visit number	Visit name	Planned day of the visit
1	1	1	2	Baseline	1
2	57	56	3	4 weeks	29
58	127	69	5	12 weeks	85
128	No limit		7	24 weeks	169

[1] First trial drug intake date is taken into account as a reference to calculate time windows

## **7. PLANNED ANALYSIS**

For End of Text tables, the set of summary statistics is: N / Mean / SD / Min / Median / Max.

Tabulations of frequencies for categorical data will include all possible categories and will display the number of observations in a category as well as the percentage (%) relative to the respective treatment group (unless otherwise specified, all patients in the respective patient set whether they have non-missing values or not). Percentages will be rounded to one decimal place. The category missing will be displayed as the last category only if there are actually missing values.

#### **7.4 PRIMARY ENDPOINT**

Please refer to Section 7.3.1 of the CTP.

### **7.4.1 Primary analysis**

The primary analysis will be done on the TS in observed cases including observations after premature discontinuation of treatment.

All visits from baseline to week 12 will be included in the primary analysis, after time-windowing. Measurements after week 12 are not taken into consideration for this endpoint.

A patient is considered as having signs indicative of right heart dysfunction if at least one of the conditions presence of right ventricular dilatation, paradoxical septum motion, right atrium enlargement, right ventricular systolic dysfunction, or right ventricular hypertrophy is met.

If the null hypothesis of no difference in the mean change from baseline in SGRQ total score at week 12 between nintedanib co-administered with sildenafil compared to treatment with nintedanib alone is rejected at the two-sided alpha level of 5%, the secondary endpoints UCSD SOBQ at week 12, SGRQ total score at week 24, and UCSD SOBQ at week 24 are tested hierarchically as described in Section 7.2 of the CTP.

As defined in Section 7.3.1 of the CTP, change from baseline in SGRQ total score at week 12 will be analysed using REML based MMRM. The model will include fixed effect for treatment, visit and presence of any echocardiographic signs indicative of right heart dysfunction (as described in [Section 5.4.1.4](#)), baseline SGRQ total score as a covariate and treatment-by-visit and baseline-by visit as interaction terms. Baseline SGRQ total score will be measured at visit 2. No imputation is planned if this assessment is not available for a patient. An unstructured (co)variance matrix will be used to model the within-patient measurements. In case there is a lack of convergence, a Compound Symmetry (co)variance matrix will be used. The Roger-Kenward approximation will be used to estimate denominator degrees of freedom. Data collected after visit 5 (planned 12 weeks after start of study treatment) will not be used for this analysis. Analyses will be implemented using SAS® Version 9.4 or higher. The primary treatment comparisons will be the contrast between treatments at 12 weeks.

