Clinical Trial Protocol

Document Number:		c03484701-03
EudraCT No.:	2015-002619-14	
BI Trial No.:	1199.36	
BI Investigational Product:	Nintedanib (Ofev [®])	
Title:	INSTAGE [™] : A 24-week, double-blind, randomized, parallel-group study evaluating the efficacy and safety of oral nintedanib co-administered with oral sildenafil, compared to treatment with nintedanib alone, in patients with idiopathic pulmonary fibrosis (IPF) and advanced lung function impairment	
Brief Title:	Efficacy and safety of nintedanib co-administered with sildenafil in IPF patients with advanced lung function impairment	
Clinical Phase:	III b	
Trial Clinical Monitor:	Phone : _____ Fax : _____	
Coordinating Investigator:	Phone _____ ext _____ (Division), _____ (Clinic) Fax _____	
Status:	Revised Protocol based on Global Amendment 2	
Version and Date:	Version:	Date:
	3.0	18 AUG 2016
Page 1 of 100		
Proprietary confidential information. © 2016 Boehringer Ingelheim International GmbH or one or more of its affiliated companies. All rights reserved. This document may not - in full or in part - be passed on, reproduced, published or otherwise used without prior written permission.		

CLINICAL TRIAL PROTOCOL SYNOPSIS

Name of company:		Boehringer Ingelheim		
Name of finished product:		Ofev [®]		
Name of active ingredient:		Nintedanib		
Protocol date: 30 Dec 2015	Trial number: 1199.36		Revision date: 18 Aug 2016	
Title of trial:	INSTAGE [™] : A 24-week, double-blind, randomized, parallel-group study evaluating the efficacy and safety of oral nintedanib co-administered with oral sildenafil, compared to treatment with nintedanib alone, in patients with idiopathic pulmonary fibrosis (IPF) and advanced lung function impairment			
Coordinating Investigator:	Phone _____ ext _____ (Division), _____ (Clinic) Fax _____			
Trial sites:	Multi-centre trial			
Clinical phase:	III b			
Objective(s):	To assess efficacy and safety of concomitant treatment with nintedanib and sildenafil in IPF patients with advanced lung function impairment.			
Methodology:	Double-blind, randomized, parallel design comparison of nintedanib 150 mg bid and sildenafil 20 mg tid to nintedanib 150 mg bid and placebo matching sildenafil tid over 24 weeks			
No. of patients:				
total entered:	250 patients			
each treatment:	Randomization 1:1 125 patients assigned to each treatment arm.			
Diagnosis :	Idiopathic Pulmonary Fibrosis (IPF)			
Main criteria for inclusion:	Written informed consent;			

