Step 4	H_{03} : There is no difference in the mean change from baseline in UCSD SOBQ at week 24 between nintedanib co-administered with sildenafil compared to treatment with nintedanib. H_{a3} : There is a difference in the mean change from baseline in UCSD SOBQ at week 24 between nintedanib co-administered with sildenafil compared to treatment with nintedanib.

The hypotheses will be tested using 5% level of significance (two-sided test). Global type I error will be not exceed 5% within this procedure, thus no adjustment for multiplicity is required.

Statistical tests performed for any other endpoints not included in the above defined testing procedure will also be done only for exploratory purposes.

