7.3.2 Secondary endpoint analyses

Change from baseline in UCSD SOBQ at week 12 will be analysed using the same method as the primary endpoint, but with baseline UCSD SOBQ instead of SGRQ total score as covariate. Data collected after visit 5 (planned 12 weeks after start of study treatment) will not be used for this analysis.

Both changes from baseline in SGRQ and UCSD SOBQ at week 24 will be analysed as in the respective week 12 analysis. For these analyses, data collected from the complete 24 weeks treatment period will be used.

Percentages of patients with on-treatment SAEs from baseline to week 24 will be compared using the Cochran-Mantel-Haenszel test adjusting for the categorical covariate presence of any echocardiographic signs indicative of right heart dysfunction (yes/no). Adjusted Mantel-Haenszel type risk ratios and risk differences with 95% confidence intervals will be used to quantify the treatment effect for the comparison between treatment groups.

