7.7 DETERMINATION OF SAMPLE SIZE

The hypothesis for expected difference in the change from baseline in SGRQ total score at week 12 is -4.5 units between nintedanib co-administered with sildenafil compared to treatment with nintedanib alone using a two group t-test with a 0.025 one-sided significance level.

The assumed difference is based on observations made in the INPULSIS[®] trials, where the observed mean change from baseline to week 12 in SGRQ total score when treated with nintedanib alone was 0.75/0.05 units with a standard deviation of 12.93/11.64 (INPULSIS[®]-1/INPULSIS[®]-2).

Based on the STEP-IPF trial [[R12-3686](#)], the mean change from baseline to week 12 in SGRQ total score when treated with sildenafil alone was -4.08 units with an estimated standard deviation of 11.02 units. It is assumed that the observed treatment effect remains stable when nintedanib is co-administered with sildenafil.

Therefore, power calculations are made based on the assumption of equal standard deviations among groups and an expected difference of -4.5 units.

Table 7.7: 1 presents the different scenarios for the sample size calculation.

Table 7.7: 1 Sample size calculations for difference in the change from baseline in SGRQ total score at week 12 assuming a group difference of -4.5 units for several standard deviations and a 1:1 randomisation ratio using a two group t-test with a 0.025 one-sided significance level.

	Standard deviation	N per group	Total sample size
80% power			
	11	95	190
	12	113	226
	13	132	264
90% power			
	11	127	254
	12	150	300
	13	177	354

So, a sample size of 125 patients in both groups will have about 90% power to detect a difference in means of -4.5 units in change from baseline in SQRG total score assuming that

the common standard deviation is 11 units using a two group t-test with a 0,025 one-sided significance level.

As we use a mixed model, including adjustment for several variable, this sample size based on t-test should provide at least 90% power.

Calculations were performed using nQuery Advisor[®] 6.1 statistical package by Statistical Solutions Ltd.

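### If the unstructured MMRM does not converge, the only fallback is compound symmetry, whose standard error is too small when the variance of change is larger at the tested visit than at earlier visits

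*SAP*

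**What the plan says.** Protocol 7.3.1 and SAP 7.4.1 describe the primary model in the same terms: a REML-based MMRM with an unstructured within-patient covariance matrix and Kenward-Roger degrees of freedom. The only provision for failure is "In case there is a lack of convergence, a Compound Symmetry (co)variance matrix will be used".

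Protocol 7.3.2 gives SOBQ at week 12 the same method as the primary endpoint and adds: "Both changes from baseline in SGRQ and UCSD SOBQ at week 24 will be analysed as in the respective week 12 analysis". The rule therefore governs all four tests in the hierarchy of Protocol 7.2, each at a two-sided 5% level.

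The SGRQ and SOBQ are taken at baseline and weeks 4, 12 and 24 (protocol flow chart, SAP Table 6.7: 2). The week-12 models thus have two response visits (weeks 4 and 12) and the week-24 models three. Baseline enters as a covariate.

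The published text names no change of optimiser or parameterisation, no intermediate structure and no empirical (sandwich) variance. That the fallback would use model-based errors is my reading of the Kenward-Roger specification; the documents do not use that term.

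**The concern.** Compound symmetry assumes one variance for all visits and one correlation for all pairs. The tested contrast always lies at the last visit in the model. If the variance of change is larger there, compound symmetry averages it with smaller earlier variances and reports too small a standard error. Kenward-Roger allows for the uncertainty in estimating covariance parameters; it does not repair a wrong covariance structure. A confirmatory test run this way could reject a true null more often than 5% of the time.

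The step is also larger than the problem it answers. A two-visit unstructured matrix has 2 × 3 / 2 = 3 parameters and a three-visit matrix 3 × 4 / 2 = 6. With about 250 patients, a failure would most likely be numerical, and other numerical routes could keep the intended model.

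**Working it through.** **The plan's own figure.** Protocol 7.7 states: "So, a sample size of 125 patients in both groups will have about 90% power to detect a difference in means of -4.5 units", with SD 11 and one-sided 0.025. The standard error is 11 × sqrt(2/125) = 1.391, and 4.5 / 1.391 = 3.234. Normal power is Φ(3.234 − 1.960) = 89.9%; the noncentral t gives 89.6%. The stated power is reproduced.

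**What the documents give on variance.** Protocol 7.7 has week-12 SDs only. For nintedanib alone in the two INPULSIS trials, the mean changes were "0.75/0.05 units with a standard deviation of 12.93/11.64"; for sildenafil in STEP-IPF the SD was 11.02. There is no SD for week 4 or week 24 and no between-visit correlation. Every SD pattern below is an assumption.

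**Formula.** With complete data and a treatment-by-visit term, the estimated contrast at visit t is in essence the adjusted difference in means at that visit. Its true variance is proportional to the variance at t. Compound symmetry replaces this with the average of the visit variances. Hence:

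- SE ratio (reported / true) = sqrt(mean of visit variances / variance at t)
- actual two-sided error = 2 × (1 − Φ(1.96 × SE ratio))

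For week 12 with r = SD(week 4) / SD(week 12), the ratio is sqrt((1 + r²)/2). At r = 0.8 it is sqrt(0.82) = 0.906, and 2 × (1 − Φ(1.775)) = 7.6%.

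For week 24 with SDs 0.8:1:1.2, the mean variance is (0.64 + 1 + 1.44)/3 = 1.027. The ratio is sqrt(1.027/1.44) = 0.844, giving 9.8%.

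**Simulation check.** The planned mean model was fitted by REML under compound symmetry: 125 per arm, 4,000 trials per scenario, no treatment effect, week-12 SD 11. Assumed correlations were 0.6 (two visits) and 0.5 to 0.65 (three visits). Assumed random dropout was 5%/12% or 5%/12%/25%. A t distribution with 246 df stood in for Kenward-Roger.

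| Tested visit | Assumed SD pattern | SE ratio | Error, formula | Simulated, complete | Simulated, dropout |
|---|---|---|---|---|---|
| Week 12 | 1.1:1 | 1.051 | 3.9% | 3.5% | 4.2% |
| Week 12 | 1:1 | 1.000 | 5.0% | 4.6% | 4.7% |
| Week 12 | 0.9:1 | 0.951 | 6.2% | 6.5% | 6.7% |
| Week 12 | 0.8:1 | 0.906 | 7.6% | 6.7% | 7.5% |
| Week 12 | 0.7:1 | 0.863 | 9.1% | 9.4% | 9.4% |
| Week 24 | 1:1:1 | 1.000 | 5.0% | 4.7% | 5.5% |
| Week 24 | 0.9:1:1.1 | 0.912 | 7.4% | 7.3% | 7.1% |
| Week 24 | 0.8:1:1.2 | 0.844 | 9.8% | 10.3% | 10.3% |

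The Monte Carlo standard error is about 0.35 points at 5%. In the last row with complete data, the mean reported standard error was 1.41 against a true 1.70.

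**Check of a repair.** With a sandwich variance under the same compound symmetry fit, the simulated error was 4.6% to 5.6% in every scenario.

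**The case against.** The strongest reply is that the trigger is remote. In a small check outside SAS, the planned mean model with an unstructured matrix converged in 240 of 240 simulated trials, under assumed dropout and correlations of 0.6 or 0.9. The week-24 tests are more remote still, since they are confirmatory only if the earlier steps reject. This stands, and it is why the point is minor.

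Second, nothing in the documents shows that variance grows. Protocol 1.1 describes patients who progress at different speeds, which makes divergence over time plausible but does not establish it. This also stands: constant variance gives 5%, and falling variance makes the test conservative.

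Third, the plan already has a deterministic fallback, and a list of loose alternatives would add discretion to a confirmatory test. That is fair, and any replacement must be a single ordered sequence with its degrees of freedom named. It does not defend the present rule, which is valid only if the variances happen to be suitable.

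A reader might go further and infer that use of the fallback by itself breaks the 5% level, or that it contradicts the type I error statement in Protocol 7.2. The documents support neither. The first needs growing variance as well. The second misreads 7.2, which says that the fixed order of tests needs no multiplicity adjustment; it makes no claim about a misspecified covariance.

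**Conclusion.** The point holds conditionally. Two things must both happen: the unstructured fit fails, and the variance of change is larger at the tested visit than at earlier ones. Then the two-sided error is about 6 to 9% at week 12 for SD ratios of 0.9 to 0.7, and about 7 to 10% at week 24 for the two growth patterns shown.

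These sizes rest on assumed SD patterns, and the simulations also on assumed correlations and dropout. Dropout in the simulations was random, so they say nothing about bias when missingness depends on earlier outcomes. Because the first condition is unlikely, the expected effect on the trial is small. This is a cheap gain in robustness; the main analysis is not in error.

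**What to change.** Replace the fallback sentence in Protocol 7.3.1 and SAP 7.4.1 with one ordered sequence, moving on only if the previous step fails to converge:

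1. Refit the unstructured matrix with Fisher scoring, then with a Cholesky (FA0) parameterisation, keeping Kenward-Roger.
2. For the three-visit week-24 models only, use heterogeneous Toeplitz, then heterogeneous compound symmetry, with Kenward-Roger. With two visits, heterogeneous compound symmetry is the same model as unstructured, so this step adds nothing at week 12.
3. As last resort, use compound symmetry with empirical (sandwich) standard errors and between-within degrees of freedom.

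The cost is one sentence in each document, fixed before unblinding. The downside lies in step 3: Kenward-Roger is not available there, and sandwich errors correct the standard error but not any bias from a misspecified covariance when data are missing at random.

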## **7.5 SECONDARY ENDPOINTS**

### **7.5.1 Key secondary endpoints**

Not applicable.

### **7.5.2 Secondary endpoints**

The analysis will be performed as defined in Section 7.3.2 of the CTP.

The variable ‘signs indicative of right heart dysfunction’ (yes/no) is derived as described for the primary endpoint.

For SGRQ total score and UCSD SOBQ, a graph of the mean total score change from baseline ( $\pm$  SEM) over time for each treatment group will be displayed. The same graph will be performed on adjusted mean changes from baseline.

Descriptive statistics for SGRQ total score and subscores as well as SOBQ over time and change from baseline will be displayed.

## **7.8 SAFETY ANALYSIS**

All safety analyses will be performed on the TS.

### **7.8.1 Adverse events**

Unless otherwise specified, analyses of adverse events will be descriptive in nature and will be based on BI standards (6). No hypothesis testing is planned. All analyses of AEs will be based on the number of patients with AEs and NOT on the number of AEs.

Furthermore, for analysis of AE attributes such as duration, severity, etc. multiple AE occurrence data on the CRF, will be collapsed into AE episodes provided that all of the following applies:

- The same MedDRA lowest level term was reported for the occurrences
- The occurrences were time-overlapping or time-adjacent (time-adjacency of 2 occurrences is given if the second occurrence started on the same day or on the day after the end of the first occurrence)
- Treatment did not change between the onset of the occurrences OR treatment changed between the onset of the occurrences, but no deterioration was observed for the later occurrence

For further details on summarization of AE data, please refer to the guideline “Analysis and Presentation of Adverse Event Data from Clinical Trials” (6).

The analysis of adverse events will be based on the concept of treatment emergent adverse events. That means that all adverse events occurring between first drug intake until 28 days after last drug intake (end of the residual effect period) will be assigned to the randomised treatment. Adverse events that start before first drug intake and deteriorate under treatment will also be considered as ‘treatment-emergent’.

All adverse events occurring before first drug intake and do not deteriorate under treatment will be assigned to ‘screening’ or ‘post-randomisation’ and all adverse events occurring after last drug intake will be assigned to ‘residual effect period’, ‘post-study’ or ‘follow-up’ (for listings only). Also, all AEs occurring between the start of an interruption and the end of interruption will be assigned to ‘off-treatment’ period in the listings. For details on the treatment definition, see [Section 6.1](#).

According to ICH E3 (7), AEs classified as ‘other significant’ will include those non-serious and non-significant adverse events which

- represents a marked hematological or other laboratory abnormality;
- led to an intervention, including withdrawal of drug treatment, dose reduction (‘action taken = discontinuation’ or ‘action taken = reduced’ for any of the study treatments), or significant additional concomitant therapy.

An overall summary of adverse events will be presented.

Separate tables will be provided for

- patients with adverse events occurring with an incidence in preferred term greater than 5% (in at least one treatment arm)
- patients with investigator defined drug related adverse events
- patients with serious adverse events
- patients with investigator defined drug related serious adverse events
- patients with other significant adverse events according to ICH E3 (7)
- patient with adverse events of special interest (AESI) (as defined in the CTP Section 5.3.6.1).
- patients with adverse events leading to death
- patients with adverse events leading to temporary or permanent dose reduction of nintedanib
- patients with adverse events leading to permanent dose reduction of nintedanib
- patients with adverse events leading to interruption of nintedanib
- patients with adverse events leading to interruption of sildenafil/placebo
- patients with adverse events leading to premature discontinuation of nintedanib only,
- patients with adverse events leading to premature discontinuation of sildenafil/placebo only,
- patients with adverse events leading to permanent discontinuation of nintedanib and sildenafil/placebo

These AE tables will be displayed in total and by subgroup presence (yes/no) of signs indicative of right heart dysfunction.

The system organ classes will be sorted according to the standard sort order specified by EMA, preferred terms will be sorted by frequency in oral nintedanib coadministered with oral sildenafil treatment arm (within system organ class).

Specific tables will be created in order to describe diarrhoea events:

- Display of the diarrhoea specific page of the CRF
- Summary of diarrhoea events including time to onset, number and duration of episodes
- Summary of diarrhoea adverse events including seriousness, clinical consequences (dose reduction, drug discontinuation or drug interruption) and outcome

Also, a Kaplan-Meier plot of time to first diarrhoea event will be drawn by treatment.

Specific summary tables including seriousness, clinical consequences and outcome will also be presented to describe the bleeding adverse events. Depending on the number of patients having such adverse events, summary tables including time to onset, number of episodes and duration may also be produced.

In addition, the number of treatment emergent MACE events will be displayed including result of adjudication overall and by presence (yes/no) of signs indicative of right heart dysfunction.

The following adverse event groupings have been defined outside the trial protocol:

Table 7.8.1: 1 Adverse events by system using aggregated terms

System	Safety Topic	Definition (selection criteria)
Gastro-intestinal	Diarrhoea	PT Diarrhoea
	Nausea	PT Nausea
	Vomiting	PT Vomiting
	Abdominal pain	HLT 'Gastrointestinal and abdominal pains (excl oral and throat)
	Pancreatitis	SMQ Acute pancreatitis (narrow)
	Gastrointestinal perforation	SMQ Gastrointestinal perforation (narrow)
Hepato-biliary	Drug-induced liver injury (DILI)	PT Drug-induced liver injury
	Hepatic disorders combined	Table to show cumulative row for all 4 SMQs below, followed by a cumulative row for each subSMQ, followed by all PTs driving that subSMQ  SMQ Drug related hepatic disorders – comprehensive search (narrow) OR SMQ Liver related investigations, signs and symptoms (broad) OR SMQ Cholestasis and jaundice of hepatic origin (narrow) OR SMQ Hepatitis, non-infectious (narrow)
	Hepatic failure	SMQ Hepatic failure, fibrosis and cirrhosis and other liver damage-related conditions (narrow)
Cardio-vascular	Arterial thromboembolism	SMQ Embolic and thrombotic events, arterial (narrow)
	Myocardial infarction	SMQ Myocardial infarction (narrow)

Table 7.8.1: 1 Adverse events by system using aggregated terms (continued)

System	Safety Topic	Definition (selection criteria)
Cardio-vascular	Stroke	Pharmacovigilance Endpoint Stroke PTs (see list in ADS Plan)
	Haemorrhagic stroke	SMQ Haemorrhagic central nervous system vascular conditions (narrow)
	Ischaemic stroke	SMQ Ischaemic central nervous system vascular conditions (narrow)
	Stroke (broad)	SMQ Haemorrhagic central nervous system vascular conditions (narrow) OR SMQ Ischaemic central nervous system vascular conditions (narrow)
	MACE	Fatal events in SOC Cardiac OR  Fatal events in SOC Vascular OR  Any fatal or nonfatal events in SMQ Myocardial infarction (narrow) OR  PTs Cardiac death, Sudden death, Sudden Cardiac death OR  Any fatal or nonfatal events as defined in PV Endpoint Stroke PTs
	Cardiac failure	SMQ Cardiac failure (narrow)
	QT prolongation	SMQ Torsade de pointes/QT prolongation (narrow)
	Venous thromboembolism	SMQ Embolic and thrombotic events, venous (narrow)
	Pulmonary embolism	PT Pulmonary embolism
	DVT	PT Deep vein thrombosis
Hypertension	SMQ Hypertension (narrow)	
Metabolic	Decreased appetite	PT Decreased appetite
	Weight decreased	PTs: Weight decreased, Abnormal loss of weight

Table 7.8.1: 1 Adverse events by system using aggregated terms (continued)

System	Safety Topic	Definition (selection criteria)
Blood	Bleeding	SMQ Haemorrhage terms (excl. laboratory terms) (narrow) displayed in total and then according to categories (see list in ADS Plan): 
 
• Gastrointestinal – oral
 
• Gastrointestinal – upper
 
• Gastrointestinal – lower
 
• Gastrointestinal – nonspecific
 
• Skin
 
• Respiratory
 
• CNS
 
• Urogenital
 
• Other
 

	GI bleeding – oral	
	GI bleeding – upper	
	GI bleeding – lower	
	GI bleeding – nonspecific	
	Skin bleeding	
	Respiratory bleeding	
	CNS bleeding	
	Urogenital bleeding	
	Other bleeding	
	Thrombocytopenia	PTs: Thrombocytopenia, Platelet count decreased, Immune thrombocytopenic purpura
	Haematopoietic thrombocytopenia	SMQ Haematopoietic thrombocytopenia (broad)
	Neutropenia	SMQ Agranulocytosis (narrow) OR SMQ Haematopoietic leukopenia (narrow)
Renal	Renal failure	SMQ Acute renal failure (narrow)
	Proteinuria	SMQ Proteinuria (narrow)
	Glomerulonephritis (broad)	SMQ Chronic kidney disease (broad)
	Glomerulonephritis (narrow)	HLT Glomerulonephritis and nephrotic syndrome
Psychiatric	Depression	SMQ Depression (excl suicide and self-injury) (narrow)
	Suicide	SMQ Suicide/self-injury (narrow)

Table 7.8.1: 1 Adverse events by system using aggregated terms (continued)

System	Safety Topic	Definition (selection criteria)
Cutaneous	Rash	BICMQ Skin rash (narrow): Exfoliative rash Mucocutaneous rash Rash Rash erythematous Rash follicular Rash generalized Rash macular Rash maculo-papular Rash maculovesicular Rash morbilliform Rash neonatal Rash papular Rash papulosquamous Rash pruritic Rash pustular Rash rubelliform Rash scarlatiniform Rash vesicular Symmetrical drug-related intertriginous and flexural exanthema Vascular access site bruising
	Pruritus	PT Pruritus
	Severe skin reactions	SMQ Severe cutaneous adverse reactions (narrow)
Liver laboratories	Hepatic enzyme increased	Alanine aminotransferase abnormal Alanine aminotransferase increased Aspartate aminotransferase abnormal Aspartate aminotransferase increased Hepatic enzyme abnormal Hepatic enzyme increased Hepatic function abnormal Hypertransaminasaemia Liver function test abnormal Transaminases abnormal Transaminases increased Blood alkaline phosphatase abnormal Blood alkaline phosphatase increased Gamma-glutamyltransferase abnormal Gamma-glutamyltransferase increased

Table 7.8.1: 1 Adverse events by system using aggregated terms (continued)

System	Safety Topic	Definition (selection criteria)
Liver laboratories	Hyperbilirubinaemia	Blood bilirubin abnormal Blood bilirubin increased Blood bilirubin unconjugated increased Hyperbilirubinaemia Icterus index increased Jaundice Jaundice hepatocellular Bilirubin conjugated abnormal Bilirubin conjugated increased
	Alanine aminotransferase increased	Alanine aminotransferase increased Alanine aminotransferase abnormal
	Aspartate aminotransferase increased	Aspartate aminotransferase increased Aspartate aminotransferase abnormal
	Gamma-glutamyl-transferase increased	Gamma-glutamyltransferase increased Gamma-glutamyltransferase abnormal
	Blood alkaline phosphatase increased	Blood alkaline phosphatase increased Blood alkaline phosphatase abnormal

For definitions of Pharmacovigilance Endpoint **Stroke** PTs and for **SMQ haemorrhage** term categorization see ADS plan.

All these definitions are based on MedDRA version 20.1. Note that changes to these definitions due to MedDRA updates will not trigger a TSAP update. Updated definitions are maintained in BIRDS under Human Pharma/nintedanib/Clinical/substance level/Project Data Management and Statistics/Section 4 Database.

The most recent version effective at DBL date will be used for trial reporting.

Frequencies and percentages of patients with AEs within system and within safety topic according to aggregated terms will be presented by treatment arm. The data will be displayed according to the order given in [Table 7.8.1: 1](#).

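### The Rash topic in SAP Table 7.8.1:1 includes a bruising term, so a patient with only an access-site bruise would be counted as having rash; separately, one renal row carries a label that does not match its query.

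*SAP*

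**What the plan says.** Table 7.8.1:1 in SAP section 7.8.1 groups adverse events into safety topics. The SAP introduces it with "The following adverse event groupings have been defined outside the trial protocol". Its use is stated after the table: "Frequencies and percentages of patients with AEs within system and within safety topic according to aggregated terms will be presented by treatment arm".

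- **Rash (Cutaneous).** The selection is "BICMQ Skin rash (narrow" scope, with the terms written out. The last one is "Vascular access site bruising".
- **Bleeding (Blood).** A separate topic built on a haemorrhage query and split into categories, one of which is Skin. The allocation of terms to categories is kept in the ADS plan.
- **Glomerulonephritis (broad) (Renal).** Selected by "SMQ Chronic kidney disease (broad" scope.
- **Glomerulonephritis (narrow) (Renal).** The next row, selected by "HLT Glomerulonephritis and nephrotic syndrome".

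The notes under the table say that the definitions rest on MedDRA 20.1, that changes caused by MedDRA updates will not lead to a new SAP version, and that updated definitions are kept in a substance-level file. They add: "The most recent version effective at DBL date will be used for trial reporting". On adverse events generally, section 7.8.1 says "No hypothesis testing is planned".

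**The concern.** A safety-topic row is read by its label. A reader of the rash row will take the percentage as patients with a rash. A bruise at a vascular access site is a different kind of event, and the table already has a skin category under Bleeding where it would more naturally belong. Bleeding is also a stated nintedanib risk (Protocol sections 1.2.1 and 2.3), so it matters that bruising and rash are kept apart.

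At stake is the accuracy of a few descriptive rows. They carry some weight because Protocol section 2.2 names enlargement of the nintedanib safety database in this population as a further important objective, so topic rows may be set beside those of other nintedanib trials. With about 125 patients per arm, one or two misplaced patients are visible in a row with a small count.

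The renal row raises a milder question. Its label names one disease and its query names another, wider condition, so a reader who sees only the output table could misread what was counted.

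**Working it through.** There is no stated figure to reproduce. The check compares labels with selection rules and then scales the effect of one patient.

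**1. Rash list.** The terms printed under Rash are:

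- exfoliative rash, mucocutaneous rash and rash (3);
- rash with a qualifier: erythematous, follicular, generalized, macular, maculo-papular, maculovesicular, morbilliform, neonatal, papular, papulosquamous, pruritic, pustular, rubelliform, scarlatiniform, vesicular (15);
- one drug-related exanthema (1).

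That gives 3 + 15 + 1 = 19 on-topic terms. The twentieth is "Vascular access site bruising". It is the only bruising term, the query is labelled narrow, and the SAP gives no reason for including it.

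**2. Does the update note remove it?** The note frees the sponsor from revising the SAP when a definition changes because of a MedDRA update. An off-topic term is not a MedDRA version change. The file in force at database lock might no longer contain the term, but nothing in the documents shows that.

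**3. Size per patient.** Section 7.8.1 counts patients, not events. The planned number is 125 per arm (Protocol synopsis). Let k be the number of patients in an arm who have the bruising term and none of the 19 rash terms. The addition to that arm's rash percentage is 100 × k/125:

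| k | Added to rash incidence |
|---|---|
| 0 | 0 |
| 1 | 0.8 percentage points |
| 2 | 1.6 percentage points |
| 3 | 2.4 percentage points |

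The documents give no event rates, so k is unknown. A patient with both a rash term and the bruising term is counted once either way and adds nothing.

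**4. Renal rows.** The broad row is selected by "SMQ Chronic kidney disease (broad" scope and the narrow row by "HLT Glomerulonephritis and nephrotic syndrome". Two other rows in the table use the tag (broad). Stroke (broad) joins the haemorrhagic and ischaemic central nervous system queries, so it widens within its named topic. Haematopoietic thrombocytopenia (broad) carries its query's own name. Glomerulonephritis (broad) does neither: it takes the name of one condition and the query of another. No row is labelled chronic kidney disease.

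**The case against.** The case on the other side has several parts.

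- **Limited reach.** The rows are descriptive. They do not enter the primary endpoint, the hierarchical tests or the SAE endpoint, and neither topic is an adverse event of special interest (Protocol section 5.3.6.1 names gastrointestinal perforation and hepatic injury). Adverse events are also tabulated by preferred term (Protocol section 7.3.4), so the bruise stays visible under its own name. This stands and makes the point minor.
- **The governing list is not visible.** The groupings were set outside the protocol, and neither the substance-level file nor the ADS plan is among the documents. The term may already be gone, or may already sit under Bleeding, Skin. This stands, and it is why the fix starts with a check.
- **Coding.** Laboratory tests are scheduled at every treatment-period visit (Protocol flow chart), and Protocol section 5.3.3 specifies venous blood. It is tempting to infer that venepuncture bruises will add to the rash count. The documents do not say that such bruises would be coded to this term, so no frequency can be derived from the visit schedule.
- **The renal row.** A reader might infer that the broad row reports a wrong glomerulonephritis incidence. The documents do not support that. The row is marked (broad), the SAP prints its query beside it, the topic-specific narrow row follows, and the terms in the chronic kidney disease query are not given. Eligibility down to a creatinine clearance of 30 mL/min does not show it either. Conditions present before inclusion are baseline conditions (Protocol section 5.3.7), and the analysis counts events that start or deteriorate under treatment. What remains is a label that does not match its query.

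None of this explains a bruising term in a list labelled narrow skin rash.

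**Conclusion.** The point on Rash holds. As the SAP is written, a patient whose only listed event is the bruising term is counted in the rash incidence, at 0.8 percentage points per such patient with 125 per arm. The effect is zero if no such patient occurs. This assumes that the printed list is the one programmed and that the arms reach their planned size.

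The renal point holds as a labelling matter only.

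It would go too far to say that either row will report a wrong incidence: event rates, the contents of the chronic kidney disease query and the definitions in force at database lock are all outside the documents. Nor do they show that any miscount would fall more on one arm than the other. The whole point is a low-priority correction.

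**What to change.** **Rash.** Check the source list of the custom query to see whether the bruising term belongs to it or entered the SAP by mistake. Delete the term from the Rash definition in Table 7.8.1:1 and from the search-category file. Confirm that the ADS plan places it under Bleeding, Skin category, and add it there if it does not.

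**Renal.** Rename Glomerulonephritis (broad) so that the row carries the name of its query, or keep the label and add a footnote that states the query and why it was chosen. Leave the narrow row as the glomerulonephritis-specific count.

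**Cost.** Two small edits to a SAP table and the matching file, with no new data. The downside is a departure from the project-level topic list, which needs a footnote wherever these rows are compared with other nintedanib trials.
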